Statistical methods	Data will be statistically analysed using GraphPad Prism v10.1.2 (La Jolla, USA). Outcomes will be tested for significant within-group and between-group differences in pre-intervention and post-intervention means using two-way analysis of variance (ANOVA). Additionally, mean change in outcomes will be tested for statistical significance between the two groups using the independent samples t-test (or non-parametric alternative if data are not normally distributed).

ABBREVIATIONS

ABCD	Association of British Clinical Diabetologists
ACCP	American College of Chest Physicians
AE	Adverse Event
ANOVA	Analysis of variance
AT	Aerobic threshold
ATS	American Thoracic Society
BIA	Bioimpedance analysis
BMI	Body mass index
CI	Chief Investigator overall
COMAP	Centre Of Metabolism, Ageing & Physiology
COPD	Chronic obstructive pulmonary disease
CPET	Cardiopulmonary exercise test
CRF	Case Report Form
CV	Curriculum vitae
DMC	Data Monitoring Committee
ECG	Electrocardiogram
ELISA	Enzyme-linked immunosorbent assay
EMG	Electromyography
GCP	Good Clinical Practice
HbA1c	Glycated haemoglobin
HIIT	High-intensity interval training
HRA	Health Research Authority
HR _{max}	Maximum heart rate
ICF	Informed Consent Form
IVGTT	Intravenous glucose tolerance test
LCD	Low calorie diet

NHS	National Health Service
PI	Principal Investigator at a local centre
PIS	Participant Information Sheet
PTR	Path to Remission
REC	Research Ethics Committee
R&D	Research and Development department
SAE	Serious Adverse Event
SD	Standard deviation
T2D	Type 2 diabetes
VLCD	Very-low calorie diet
VO _{2max}	Maximum rate of oxygen consumption

TABLE OF CONTENTS

SYNOPSIS.....	4
ABBREVIATIONS.....	6
TRIAL / STUDY BACKGROUND INFORMATION AND RATIONALE.....	10
TRIAL / STUDY OBJECTIVES AND PURPOSE	11
PURPOSE	11
PRIMARY OBJECTIVE	11
SECONDARY OBJECTIVES	12
DETAILS OF PRODUCT(S)	12
Description	12
Manufacture	12
Packaging and labelling	12
Storage, dispensing and return	12
Placebo	12
Known Side Effects	12
TRIAL / STUDY DESIGN	13
TRIAL / STUDY CONFIGURATION	13
Primary endpoint	13
Secondary endpoints	13
Safety endpoints	13
Stopping rules and discontinuation	14
RANDOMIZATION AND BLINDING	14
Maintenance of randomisation codes and procedures for breaking code	15
TRIAL/STUDY MANAGEMENT	15
DURATION OF THE TRIAL / STUDY AND PARTICIPANT INVOLVEMENT	15
End of the Trial	15
SELECTION AND WITHDRAWAL OF PARTICIPANTS	15
Recruitment	15
Eligibility criteria	16
Inclusion criteria	16
Exclusion criteria	16

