The control group will not be participating in any exercise intervention. Participants in this group will be instructed to make no significant changes to their current levels of physical activity for the 16-week period.

All participants will be advised to continue their regular medications as prescribed. These regular medications will have been recorded at the screening appointment and documented in the CRF.

Final Visit

At the end of the 16 weeks (approximately 72 hours after their final HIIT session), all participants will undergo their final study visit. This will follow the exact same format of the first study visit, except at the end of this study visit participants will be asked to complete a feedback questionnaire, thanked for their involvement and exited from the study. Subsequently, their General Practitioner will be sent a letter detailing their results with a copy also sent directly to them. If participants have any questions regarding their results and ongoing management, they will be advised to discuss these with their General Practitioner.

Compliance

Participants in the intervention group will be asked to complete an exercise documentation pack, in which they will be required to record details of each exercise session performed. They will be contacted by phone (or email) at regular intervals (at least weekly) and compliance will be one of the issues discussed, with reference to their documentation pack.

Participants will be expected to perform the HIIT sessions 3 times per week. However, this can be increased to 4 times if a session has been missed from the previous week. Compliance will be deemed acceptable if >80% of sessions are performed. Participants will be excluded if they:

- are unable to complete 4 or more consecutive sessions
- miss more than 7 sessions in total
- fail to complete the set exercise regime in 7 or more sessions

The number of participants excluded due to poor compliance will be recorded and reported in the study report and any potential publications.

Criteria for terminating trial

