Two-way analysis of variance (ANOVA) will be used to determine statistically significant differences between the mean baseline and follow-up measurements of all outcomes in both groups. Additionally, the independent samples t-test will be used to compare mean changes in outcomes between the two groups and test for statistical significant differences between them. Non-parametric alternatives will be used if data are non-normally distributed. If, despite randomisation, the mean value of an outcome at baseline is different between the groups then linear regression analysis will be performed to account for the baseline difference. The significance level will be set at $p=0.05$.

Interim analysis of available data will be performed 8-10 months into the course of the study, in order to inform the funding organisation that progress is being made. Finally, in order to maintain the safety of participants, the occurrence of adverse events will be continuously monitored and if an unacceptably high incidence of such events is noted, this will be highlighted to the Chief Investigator and Co-Investigators. At this point, a decision will be made regarding continuation of the study, or if other safety procedures are required to reduce the AE occurrence rate.

Sample size and justification

This is a pilot study, as such, no power calculation has been performed to justify sample size. However, a previous study with similar participant numbers has successfully demonstrated significant improvements in beta-cell function following a HIIT intervention (Madsen *et al.*, 2015b).

Assessment of efficacy

The primary endpoint for this study is pancreatic beta-cell function assessed during an IVGTT. Thus, the HIIT intervention will be deemed efficacious if participants in the intervention group have a significantly higher beta-cell function than those in the control group, i.e. there is a greater improvement in insulin response to intravenous glucose after the 16-week intervention than after 16 weeks of usual care. Significant difference will be determined using two-way ANOVA (or other more appropriate statistical tests) as outlined above.

The secondary endpoints will provide evidence of the efficacy of the HIIT intervention on inducing improvements in other measures of cardiometabolic health and are listed below:

- Improvement in insulin sensitivity suggested by increased insulin sensitivity index (derived from the IVGTT) and reduced HOMA2-IR

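### The efficacy rule rests on a two-way ANOVA whose form and deciding effect are not fixed and adds an open alternative; baseline adjustment, the stronger analysis, is only conditional

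*Protocol*

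**What the plan says.** Three places in the protocol describe the analysis.

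- **Synopsis, Statistical methods:** "Outcomes will be tested for significant within-group and between-group differences in pre-intervention and post-intervention means using two-way analysis of variance (ANOVA". A t-test on mean change is then added.
- **Statistics – Methods:** "Two-way analysis of variance (ANOVA) will be used to determine statistically significant differences between the mean baseline and follow-up measurements of all outcomes". This applies to each arm. The section goes on: "Additionally, the independent samples t-test will be used to compare mean changes in outcomes between the two groups". Linear regression is to account for baseline only if the baseline means turn out to differ; what counts as a difference is not defined. The significance level is 0.05.
- **Statistics – Assessment of efficacy:** HIIT is efficacious if "participants in the intervention group have a significantly higher beta-cell function than those in the control group", which the same sentence explains as "there is a greater improvement in insulin response to intravenous glucose after the 16-week intervention than after 16 weeks of usual care". The rule ends: "Significant difference will be determined using two-way ANOVA (or other more appropriate statistical tests) as outlined above".

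The values are paired. Under Final Visit, the week-16 assessment is described thus: "This will follow the exact same format of the first study visit". The protocol nowhere mentions repeated measures, matching or a participant term, and nowhere says that observations are taken as independent.

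**The concern.** A two-way ANOVA of group and visit gives three tests: group, visit, and group by visit. Only the last asks whether change differs between arms. The group effect averages each person's pre-treatment and post-treatment values, so it halves a true effect and lets chance baseline differences count as treatment difference.

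The efficacy rule does not say which of these decides. Its first clause reads like a group effect and its second like the interaction. Methods assigns the ANOVA to baseline against follow-up and gives the between-arm comparison of changes to the t-test, yet the efficacy rule settles the between-arm question by the ANOVA.

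The form matters as well. Without a participant term, the two values from one person are handled as if they came from two people, which distorts the error rate in opposite directions for different effects. The closing parenthesis of the rule leaves the choice of test open in a study whose analysis is supervised by investigators who cannot be blinded.

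**Working it through.** **Inputs from the protocol.** 20 participants allocated 1:1 (Synopsis), so n = 10 per arm; two visits; level 0.05, taken as two-sided. The protocol gives no power calculation, so there is no stated figure to reproduce.

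**Assumptions.** Normal values, the same SD s at both visits, no drop-out, within-person correlation ρ of 0.3 to 0.8, and a treatment effect of 1 SD for power. The protocol gives neither ρ nor an effect size.

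**Step 1: variances.**

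- Group effect (difference in participant averages). An ordinary ANOVA assumes s²/n; the true variance is s²(1+ρ)/n. At ρ = 0.5 and n = 10 this is 0.10s² assumed against 0.15s² true, so the test rejects too often.
- Interaction (difference in mean change). An ordinary ANOVA assumes 4s²/n; the true variance is 4s²(1−ρ)/n. At ρ = 0.5 this is 0.40s² assumed against 0.20s² true, so the test rejects too rarely.

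**Step 2: large-sample false-positive rates.**

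- Group: 2[1 − Φ(1.96/√(1+ρ))] gives 8.6% at ρ = 0.3 and 14.4% at ρ = 0.8.
- Interaction: 2[1 − Φ(1.96/√(1−ρ))] gives 1.9% at ρ = 0.3 and 0.6% at ρ = 0.5.

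**Step 3: simulation at 10 per arm** (at least 60,000 trials per setting; error df 36 for ordinary ANOVA, 18 for repeated measures).

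| | ρ = 0.3 | 0.5 | 0.7 | 0.8 |
|---|---|---|---|---|
| Ordinary, group: false-positive rate | 8.5% | 10.8% | 13.3% | 14.5% |
| Ordinary, interaction: false-positive rate | 2.1% | 0.7% | 0.1% | <0.1% |
| Ordinary, interaction: power | 31% | 29% | 25% | 22% |
| Repeated measures, group: power | 26% | 23% | 21% | 20% |
| Repeated measures, interaction (= change-score t-test): power | 43% | 56% | 78% | 92% |
| ANCOVA on baseline: power | 57% | 66% | 82% | 92% |

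The repeated-measures tests and ANCOVA all keep a false-positive rate of about 5%. At ρ = 0 the ordinary ANOVA shows no distortion.

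**Step 4: identity check.** On one simulated data set the repeated-measures interaction F and the squared t on changes were both 0.0425; the ordinary ANOVA gave 0.0106 on the same data. With two visits, the repeated-measures interaction and the planned t-test on changes are one test.

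**Step 5: why ANCOVA gains.** In large samples its variance is 2s²(1−ρ²)/n against 4s²(1−ρ)/n for change scores. The ratio is (1+ρ)/2, that is 0.65, 0.75, 0.85 and 0.90 at the four correlations. The gain is largest where the correlation is low and has nearly gone at 0.8.

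**The case against.** The name two-way ANOVA is often shorthand for the repeated-measures form, and the Synopsis, which speaks of within-group differences, fits a matched analysis. The error structure could also be settled in an SAP that is not shown. This stands: silence about the participant term is not in itself a fault, and a reader who infers that the plan treats 40 values as independent goes beyond the text.

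The efficacy sentence explains its first clause by its second, "there is a greater improvement in insulin response to intravenous glucose after the 16-week intervention than after 16 weeks of usual care", which points to the difference in change. This also stands and makes the group-effect reading the less likely one. It does not remove the problem, because the rule still names no effect. Even in the repeated-measures form, reading the group effect would leave power of 26% to 20% where the interaction has 43% to 92%.

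A valid test of change is planned, and the tests outlined earlier in Methods include it and the regression. That limits the harm. But the t-test is listed as additional, the regression is conditional, and the rule names the ANOVA first with an unspecified substitute. University statistician oversight does not settle in advance which result counts.

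The trial is a declared pilot without a power claim, so no promised power is broken. Its results are nevertheless meant to inform larger studies, and it states a significance-based efficacy rule.

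Lastly, preferring ANCOVA to a correctly paired test is a matter of efficiency, not validity. That is right, and the size of the gain is shown above.

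**Conclusion.** The point holds as a defect in what the protocol fixes. The deciding rule names an ANOVA without its form or effect, words its criterion in two ways, permits an undefined alternative, and makes baseline adjustment depend on the observed baseline means.

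The distortion figures are conditional on the ordinary form being run and on the assumed correlation, effect size and normality. In that case the group effect would reject at about 1.7 to 2.9 times the stated 5% (8.5/5 to 14.5/5). A reader might infer that the rate is always at least doubled, or that the interaction always loses most of its power. Neither follows: at ρ = 0.3 the rate is 1.7 times nominal and power falls from 43% to 31%, about a quarter; at ρ = 0.5 it falls from 56% to 29%, just under half.

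If the repeated-measures interaction was intended, the error rate is right. What is left to gain from ANCOVA is then about 14, 10 and 4 percentage points of power at ρ = 0.3, 0.5 and 0.7, and almost nothing at 0.8.

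**What to change.** In the Synopsis (Statistical methods), Statistics – Methods and Assessment of efficacy, name one deciding analysis for the primary endpoint. Suggested wording:

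> The primary analysis is the between-arm difference in beta-cell function at week 16, estimated by linear regression (ANCOVA) with arm and the baseline value as covariates, fitted whether or not baseline means differ, and tested two-sided at the 5% level.

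Then make three matching changes:

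- Delete the parenthetical alternative from the efficacy rule.
- Word the efficacy criterion once, as this baseline-adjusted difference.
- If the ANOVA is kept as supportive, call it a two-way repeated-measures ANOVA with visits matched within participant, read on the group-by-visit interaction only, and note that the change-score t-test is the same test.

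The cost is a wording amendment. The baseline value is already collected and the regression is already in the plan, so no extra measurement or participant is needed.

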Title	Can High-Intensity Interval Training (HIIT) reduce the risk of diabetes relapse following discharge from the NHS Path to Remission Programme? – a pilot study
Short title	HIIT post LCD
Chief Investigator	[name]
Objectives	To determine the effect of a 16-week home-based HIIT intervention on markers of glucose metabolism and glycaemic control in individuals with T2D that have achieved diabetes remission in the NHS Path to Remission Programme.
Trial Configuration	Parallel group, non-blinded, randomised control study
Setting	Clinical research facility (Postgraduate Centre, University of Nottingham, Derby Campus)
Sample size estimate	This is a pilot study, therefore no power calculation has been performed
Number of participants	20 participants will be recruited and allocated 1:1 into intervention or control groups
Eligibility criteria	
 • Adults between the age of 18-70 years • Ability to provide informed consent. • Completed the NHS Path to Remission programme and achieved diabetes remission (HbA1c <48mmol/mol (6.5%), and off diabetes medications for at least three months)
Description of interventions	The intervention group will participate in a 16-week HIIT programme involving 3 sessions per week in their own homes. The HIIT sessions are comprised of five 1-minute intervals of body-weight exercises interspersed with 90-second active recovery periods. The control group will continue with their usual levels of activity.
Duration of study	
Each participant will be involved in the study for 16 weeks.
 
The study is expected to commence in November 2024 and be completed by the end of August 2026.

Randomisation and blinding	Participants will be randomised to the two groups using the “sealed envelope” online software. Research staff in direct contact with participants will not be blinded, however staff involved solely in analysis of samples and data will be blinded to the randomisation of participants.
Outcome measures	
The primary endpoint for this study will be beta-cell function assessed during an intravenous glucose tolerance test (IVGTT)
 
Secondary outcome measures include:
 
 • Insulin sensitivity • Overall glycaemic control • Body weight • Body composition • Skeletal muscle function

	
 • Skeletal muscle structure • Cardiorespiratory fitness (measured as VO_{2max} during cardiopulmonary exercise testing, CPET)

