Data will be analysed within our research department based in the Division of Medicinal Sciences and Graduate Entry Medicine, at the Royal Derby Hospital campus of the University of Nottingham. Analysis will be performed primarily by [name], under the supervision of Chief Investigator and other Co-Investigators. In addition, there will be oversight provided by the university support statistician. It will not be possible to blind the study investigators to the randomisation of participants. However, staff involved solely in analysis of samples and data will be blinded to the randomisation of participants. All analysed data will be stored and backed-up within a secure online data management system on the University of Nottingham's internal server.

Data will be analysed using the statistical programmes GraphPad Prism v10.2.1 (La Jolla, California, the USA), which is available on the university internal server. Prior to statistical analysis, data will be tested for normality using the Kolmogorov-Smirnov test. Normally distributed data will be expressed as mean (SD), whilst non-normally distributed data will be reported as median \pm inter-quartile range.

The primary endpoint beta-cell function will be derived from the area-under-curve (AUC) of serum insulin concentration during the first 10 minutes of the IVGTT (Cersosimo *et al.*, 2014). This correlates well with the gold standard hyperinsulinaemic clamp (Rakotoambinina *et al.*, 1997) and can sensitively detect changes in beta cell function in response to dietary interventions (Jackness *et al.*, 2013; Liu *et al.*, 2015). Insulin sensitivity will be derived from serum glucose and insulin concentrations obtained during the IVGTT. An insulin sensitivity index developed by Tura *et al.* (Tura *et al.*, 2010) will be calculated, as well as HOMA2-IR from fasting glucose and insulin concentrations. Body composition measures (lean body mass and fat mass) will be directly determined from BIA.

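### Baseline adjustment hangs on an undefined trigger and no single test is named to decide efficacy; one pre-specified ANCOVA would remove the choice and, at most plausible correlations, add precision

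*Protocol*

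**What the plan says.** Under Statistics, Methods, the protocol lays out several routes to a result for each outcome:

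- A two-way ANOVA that compares the two visits in the two arms.
- Alongside it, a t-test for independent samples on the change from baseline.
- Non-parametric versions if the data are not normal, after a gate: "Prior to statistical analysis, data will be tested for normality using the Kolmogorov-Smirnov test".
- A regression used only on a condition: "If, despite randomisation, the mean value of an outcome at baseline is different between the groups then linear regression analysis will be performed". Neither a size nor a p-value defines the condition.

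Under Assessment of efficacy, HIIT is to be declared efficacious if beta-cell function is significantly higher than in controls, in the sense of a greater improvement. The test is left open: "Significant difference will be determined using two-way ANOVA (or other more appropriate statistical tests) as outlined above". The significance level is 0.05. The synopsis lists the ANOVA and the change t-test (or its non-parametric form) but not the baseline regression. On size, the synopsis says "20 participants will be recruited and allocated 1:1 into intervention or control groups", and the sample size section gives as its reason "This is a pilot study, as such, no power calculation has been performed to justify sample size".

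**The concern.** Two features are fixed badly in the protocol itself.

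First, the trigger for baseline adjustment cannot be applied as written. Two sample means are practically never equal, so read literally it always fires. Read as a significance test, it almost never fires in a trial of this size. Either way, someone decides after seeing the data whether the treatment estimate is adjusted.

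Second, the protocol decides efficacy by significance but does not say which test decides. The ANOVA, the change t-test, the regression and the non-parametric forms can disagree, and the clause admitting other tests leaves the list open.

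At stake is a clear primary result, and precision that a trial of 20 can ill afford to lose. The baseline values needed for a better analysis are already collected.

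**Working it through.** **Inputs.** From the protocol: 20 participants, 1:1, so n = 10 per arm; significance level 0.05. The protocol states no power, effect size, SD or baseline-to-follow-up correlation (rho), so it has no figure to reproduce. Assumed: two-sided test, bivariate normal data, equal SD at both visits, a true effect of 1 SD, and rho over a range.

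**Step 1: what a significance trigger would miss.** With 18 df the critical t is 2.101. The smallest significant baseline gap is 2.101 × √(2/10) = 0.94 SD. Gaps up to about 0.94 SD would go unadjusted.

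**Step 2: how often a sizeable gap arises by chance.** P(|gap| > 0.5 SD) = 2 × [1 − Φ(0.5/√0.2)] = 0.26.

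**Step 3: precision.** Per-participant variance in SD² units:

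- Change score: 2(1 − rho).
- ANCOVA: (1 − rho²) × [1 + 1/(2n − 4)]. The bracket is the cost of estimating the slope; here it is 1 + 1/16 = 1.0625.
- Ratio, ANCOVA to change: 1.0625 × (1 + rho)/2.

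At rho = 0.5 the change score has variance 1.00 and ANCOVA 0.75 × 1.0625 = 0.797. The standard errors of the group difference are √(1.00 × 0.2) = 0.447 SD and √(0.797 × 0.2) = 0.399 SD.

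**Step 4: power at a 1 SD effect** (simulation). With two visits, the group-by-time term of a repeated-measures ANOVA is the same test as the change t-test, so one column serves both.

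| rho | Variance ratio | Change t-test | ANCOVA |
|---|---|---|---|
| 0.3 | 0.69 | 43% | 58% |
| 0.5 | 0.80 | 56% | 66% |
| 0.6 | 0.85 | 66% | 73% |
| 0.7 | 0.90 | 78% | 82% |
| 0.8 | 0.96 | 91.6% | 92.5% |
| 0.85 | 0.98 | 97.0% | 97.1% |

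At rho = 0.9 the ratio is 1.0625 × 0.95 = 1.01, so ANCOVA no longer gains. With 8 per arm, after drop-out for example, the crossover lies between 0.80 and 0.85.

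**Step 5: the conditional rule.** Take the change test unless baselines differ, then ANCOVA, with the trigger read as p < 0.05, p < 0.20 or a gap above 0.5 SD. Power at 1 SD is 43–45% at rho 0.3, 56–58% at 0.5 and 78–79% at 0.7. The rule therefore recovers little of what ANCOVA offers. Its type I error is about 3–5%.

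**Step 6: trials with a chance imbalance.** Among the 26% of trials with a gap above 0.5 SD, the unadjusted change test has a type I error of about 11% at rho 0.3, 9.5% at 0.5, 8.5% at 0.6 and 7–8% at 0.7. ANCOVA stays at about 5%. This matters wherever the trigger is read so that such a gap goes unadjusted.

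**Step 7: choosing by result.** If the more favourable of the change test and ANCOVA were reported, type I error would be about 7%.

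**The case against.** The strongest reply is that this is a 20-person pilot without a power target, that a university statistician has oversight, and that a SAP may name the test. Part of this stands. It lowers the severity, and it makes the estimate with its interval the main gain rather than power. It does not remove the point: the protocol itself writes the conditional rule and the open clause, and it declares efficacy by significance. A SAP that fixed one analysis would have to depart from that text.

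It is also fair that ANCOVA is not always more powerful. The protocol gives no correlation, and the advantage is gone by about 0.85.

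A reader might infer more than the document supports:

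- *That the baseline trigger inflates false positives.* By itself it does not; it is slightly conservative. Inflation needs a choice that follows the results, which the text permits but does not plan.
- *That the error rate would reach 9–10%.* That needs a follow-up-only comparison as a third option. The protocol names none, and it defines efficacy as greater improvement.
- *That the ANOVA ignores pairing.* The natural reading is group by time on repeated measurements. Leaving out the words repeated-measures is a detail that a SAP commonly supplies.
- *That the Kolmogorov-Smirnov gate will pass skewed insulin data and so damage the result.* The document gives no skew, and no effect on error or power has been shown. The gate matters here only as one more data-dependent branch.
- *That within-group tests decide efficacy.* The synopsis mentions them, but the efficacy criterion is between groups.

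**Conclusion.** The point holds as a should-fix. The adjustment rule has no usable criterion, and the efficacy decision has no named primary test. Under the stated assumptions, using ANCOVA in every case adds about 15, 10, 7 and 4 percentage points of power at correlations of 0.3, 0.5, 0.6 and 0.7 (58 − 43, 66 − 56, 73 − 66, 82 − 78). It adds about 1 point at 0.8 and nothing from about 0.85 upward. These sizes rest on normal data, equal SDs, a 1 SD effect and 10 completers per arm; only the planned 10 per arm comes from the protocol. The documents do not support saying that the plan as written has an inflated type I error. The roughly 7% applies only if the choice between the two tests is made on their results.

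**What to change.** In Statistics (Methods and Assessment of efficacy) and in the synopsis:

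1. State that the primary analysis is ANCOVA of the week-16 value on randomised group and the baseline value, regardless of baseline similarity, reported as an adjusted difference with a 95% confidence interval.
2. Delete the baseline trigger and the clause that admits other, more appropriate tests.
3. Replace the Kolmogorov-Smirnov gate with an analysis scale for the insulin AUC that is set before outcome data, including the interim data, are seen. A log scale is one option if all values are positive; this needs checking, because the primary endpoint is an increment above basal and could be zero or negative.
4. Keep the ANOVA, the change t-test and a rank-based or permutation analysis as supportive only.

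The cost is wording and one degree of freedom. Visits, sample size and participant care are unchanged.

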- Blood pressure drop of >20mmHg
- Drop in heart rate >10 beats per minute
- Oxygen saturations <94%

If any of these were to occur during the CPET session then this will also be grounds for removal from the study to ensure the safety of the participants.

Participants will also be encouraged to report any injuries that occur during the exercise sessions. With all injuries, a discussion will be held to determine whether removal is appropriate, however, in the case of any injuries that requires medical intervention, an individual's participation will be discontinued.

RANDOMIZATION AND BLINDING

Participants will be recruited to the study by the Co-Investigator [name] and the Chief Investigator [name]. All participants will go through an initial screening appointment and then a final decision regarding recruitment will be made after discussion between the study investigators. Following this, they will be randomised to either the intervention or control groups by [name] using the online "Sealed Envelope" software (www.sealedenvelope.com), which is the standard method of randomisation utilised for studies in this research department. The randomisation ratio will be 1:1 and the allocation

sequence will be generated by an algorithm within the online software, and as such, will be third party.

This study will be investigating the effects of an exercise intervention. Due to the nature of this intervention and the processes required to safely monitor the intervention group, blinding of participants or study investigators will not be possible. However, any research staff involved solely in data analysis will be blinded to the group that participants are allocated to. Neither those involved in data analysis, nor the study statistician will have contact with participants.

Maintenance of randomisation codes and procedures for breaking code

Blinding of participants and research staff is not possible in this study, therefore will not be used. Thus, there will not be any randomisation codes and no need to break a randomisation code. In the event of an SAE, the group in which the participant has been allocated to will be easily accessible from the study master file, which can be accessed by the Chief Investigator or any of the Co-Investigators.

TRIAL/STUDY MANAGEMENT

The trial will be managed by a single assigned project manager. There will not be a Trial Steering Committee, Management Group or Data Monitoring Committee for this.

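### Baseline adjustment depends on an undefined, after-the-fact check of the baseline means; ANCOVA should be the stated comparison for every outcome measured at both visits

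*Protocol*

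**What the plan says.** Three places in the protocol bear on this.

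- **Synopsis, Statistical methods.** Alongside a two-way ANOVA, "mean change in outcomes will be tested for statistical significance between the two groups using the independent samples t-test". Baseline adjustment is not mentioned.
- **Statistics, Methods.** "Two-way analysis of variance (ANOVA) will be used to determine statistically significant differences between the mean baseline and follow-up measurements of all outcomes", and an independent-samples t-test compares mean changes between arms. Two exceptions follow: "Non-parametric alternatives will be used if data are non-normally distributed", and "If, despite randomisation, the mean value of an outcome at baseline is different between the groups then linear regression analysis will be performed". No threshold or test defines when baseline means count as different. Nothing says whether the regression replaces the default tests or is reported beside them.
- **Statistics, Assessment of efficacy.** The intervention is judged on the primary endpoint by two-way ANOVA, with an open allowance for another test thought more suitable.

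On size: "20 participants will be recruited and allocated 1:1 into intervention or control groups". The sample size section adds: "This is a pilot study, as such, no power calculation has been performed to justify sample size".

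**The concern.** Two sample means of a continuous measurement practically never coincide. Taken literally, the condition always holds, and the t-test presented as the main comparison would never stand alone. Taken any other way, someone must run a baseline significance test or make a judgement after seeing the data. The Methods section puts the analysis under the supervision of investigators who, it says, cannot be blinded.

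A chance baseline gap that does not trigger the rule stays in the result. A change score subtracts the whole baseline value, which is too much whenever ρ is below 1, so the arm that starts low tends to show the larger gain through regression to the mean.

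The two exceptions can also collide. For a skewed outcome with unequal baselines, one sentence leads to a rank test without adjustment and the other to linear regression. No order of precedence is given.

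At stake are precision in a 20-person trial, bias given the imbalance actually observed, and the freedom to choose the model after seeing the data.

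**Working it through.** **Inputs.** From the protocol: 20 participants, 1:1, so n = 10 per arm; significance level 0.05. Assumed, because the protocol gives none of these: two-sided testing, normal data, the same SD at both visits, a true effect of 1 SD, and ρ from 0.3 to 0.95. The protocol has no power figure to reproduce.

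**1. How often is baseline unbalanced?** The SE of the baseline difference is √(2/10) = 0.447 SD.

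- P(gap > 0.5 SD) = 2 × [1 − Φ(0.5/0.447)] = 0.264.
- P(gap > 0.25 SD) = 2 × [1 − Φ(0.25/0.447)] = 0.576.
- A p < 0.05 baseline test fires in 5% of trials by construction. With 18 degrees of freedom it needs a gap of about 2.10 × 0.447 = 0.94 SD.

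**2. What does an unadjusted gap do?** Given a baseline gap g, the change contrast is shifted by −(1 − ρ) × g. For g = 0.5 SD the size is 0.35, 0.25, 0.15, 0.10 and 0.05 SD at ρ = 0.3, 0.5, 0.7, 0.8 and 0.9.

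**3. Precision.** In SD² units the change score has variance factor 2(1 − ρ). ANCOVA has (1 − ρ²) × (1 + 1/(N − 4)), with N = 20. The ratio of ANCOVA to change score is therefore (1 + ρ)/2 × 17/16:

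| ρ | 0.3 | 0.5 | 0.7 | 0.8 | 0.9 | 0.95 |
|---|---|---|---|---|---|---|
| Variance ratio | 0.69 | 0.80 | 0.90 | 0.96 | 1.01 | 1.04 |

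The ratio equals 1 at ρ = 32/17 − 1 = 0.88. Below that ANCOVA is more precise; above it, slightly less.

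**4. Power for a 1 SD effect** (100,000 simulated trials per setting; repeat runs agree to about one point). Since the trigger is undefined, two readings were tried.

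| ρ | Change-score t-test | Regression if baseline p < 0.05 | Regression if gap > 0.5 SD | ANCOVA always |
|---|---|---|---|---|
| 0.3 | 43% | 43% | 45% | 57–58% |
| 0.5 | 56% | 56% | 58% | 66% |
| 0.7 | 78% | 78% | 78% | 81–82% |
| 0.8 | 92% | 91% | 92% | 92–93% |
| 0.9 | 99.7% | 99.6% | 99.6% | 99.6% |

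In terms of SE at ρ = 0.3, the change score gives 0.527, the p < 0.05 trigger 0.506, the 0.5 SD trigger 0.464 and ANCOVA 0.440. The 0.5 SD trigger thus recovers (0.527 − 0.464)/(0.527 − 0.440), about 70% of the SE loss, but little of the power.

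**5. Type I error.** A fixed two-step rule is conservative: about 4.1–4.9% with the p < 0.05 trigger and 3.2–4.8% with the 0.5 SD trigger. ANCOVA always gives 4.9–5.1%. If the better of the change-score and ANCOVA p-values may be reported, the rate is about 6–8%, highest at low ρ.

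**The case against.** **The default analyses already use the baseline.** This is correct. A change score, or a pre/post factor in an ANOVA, uses it with the slope fixed at 1. A reader might infer that the baseline measurement is thrown away; it is used inefficiently, and the inefficiency fades as ρ rises.

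**The loss depends on a trigger the protocol does not name.** This also stands. A reader might infer that conditional adjustment recovers almost none of the lost precision. That describes power under a p < 0.05 trigger. A gap-size trigger recovers part of the loss, and under the literal reading regression is always run and nothing is lost.

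**ANCOVA is not free.** It spends one error degree of freedom (17 instead of 18). Where ρ exceeds about 0.88, which could include body weight or lean mass (an assumption), its variance is about 1–4% higher.

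**Not every participant has a baseline for every outcome.** Under the procedures for missing data, someone in whom an IVGTT cannot be done stays in the study without primary-outcome data at either visit. Such participants contribute to the primary analysis under neither method, so the comparison of methods is unaffected.

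**This is a pilot, and details may sit in an analysis plan that is not at hand.** The power figures are indeed illustrative. But the conditional rule is stated in the protocol itself, efficacy is to be declared by significance, and the results are meant to inform larger studies.

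**Conclusion.** The point holds as a fault in the stated rule. Whether baseline is adjusted for depends on an undefined comparison made after the data are seen, and imbalance that does not trigger the rule stays in the estimate. Prespecified ANCOVA is the better method.

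The size depends on ρ and on how the trigger is read. Against the change score or the p < 0.05 reading, the gain in power is roughly 14–15 points at ρ = 0.3, 10 at 0.5, 4 at 0.7 and about 1 at 0.8; at 0.9 there is none. This rests on normal data, equal SDs and a 1 SD effect, none of which the protocol supplies.

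A reader might infer that the two-step rule inflates false positives. Applied as a fixed rule it does not; it runs somewhat below 5%. Inflation to about 6–8% arises only if the loose wording lets the more favourable p-value be reported. The protocol does not say that this will be done, but its wording does not prevent it.

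**What to change.** Delete the conditional sentence in Statistics, Methods, and put in its place wording such as:

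> The between-arm comparison for every outcome measured at both visits is an ANCOVA of the 16-week value on arm and the baseline value of the same outcome, whatever the observed baseline difference. The effect is reported as the adjusted mean difference with its 95% confidence interval. Baseline differences are not tested for significance.

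Three other places must then agree:

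- **Assessment of efficacy:** name this ANCOVA as the test that decides the primary endpoint, in place of the two-way ANOVA and its open-ended alternative.
- **Non-parametric sentence:** for skewed outcomes, state in advance a transformation to be applied before ANCOVA, replacing the unadjusted rank test. For the primary endpoint, choose one that copes with a suprabasal insulin increment at or below zero.
- **Synopsis, Statistical methods:** carry the same wording. Keep the change-score t-test and two-way ANOVA as supportive analyses only.

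The cost is a wording amendment, one error degree of freedom, and the marginal loss of precision for very stable outcomes. No extra participants, visits or measurements are needed.
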